6.3.4. Relevance Sequence Imputation

Analysis of persistently high viral load on Day 7 will utilize a relevance sequence imputation (RSI) for Treatment Arms 1-6. The RSI is defined as:

If Day 7 SARS-CoV-2 viral load is missing, then Day 7 will be imputed using a relevance sequence imputation as follows:

- 1. Impute Day 7 SARS-CoV-2 viral load with the Day 5 measurement, if available.
- 2. If Day 5 SARS-CoV-2 viral load is also missing, then impute Day 7 with the Day 3 measurement, if available.
- 3. If Day 3 SARS-CoV-2 viral load is also missing, then impute Day 7 with the Day 11 measurement, if available.
- 4. If Day 11 SARS-CoV-2 viral load is also missing, then impute Day 7 with the Day 1 measurement, if available.
- 5. If Day 1, Day 3, Day 5, Day 7, and Day 11 measurements are all missing, the viral load will be treated as MAR in the analysis.

6.3.5. Last Observation Carried Forward

Analysis of persistently high viral load on Day 7 will utilize a last observation carried forward (LOCF) analysis for Treatment Arms 7-13. The LOCF method is performed by carrying forward the last nonmissing assessment. If only the baseline viral load is nonmissing, then the baseline is carried forward.

6.3.6. Modified Last Observation Carried Forward

Analyses of symptom data, with the exception of change in symptom score, will utilize a modified last observation analysis (mLOCF). The mLOCF method is performed by carrying forward the last nonmissing postbaseline assessment to the subsequent missing assessments for analysis. For patients who die, all missing collection time points subsequent to the date of death will be imputed to Severe.

After mLOCF imputation, data from participants with nonmissing baseline and at least 1 postbaseline observation will be included in the analyses. The mLOCF imputation helps ensure that the maximum number of randomized participants who were assessed postbaseline will be included in the analyses and unfavorable terminal events are represented.

6.4. Multicenter Studies

Differences between study centers will not be a feature of the statistical analyses for this study. Baseline variables and demographics may be described by site.

Individual center results may be presented, where appropriate, when the centers have sufficient numbers of participants to make such analysis potentially valuable. The possibility of qualitative or quantitative treatment-by-center interaction may be explored.

6.5. Multiple Comparisons/Multiplicity

Treatment Arms 1-8

As this is a Phase 2 (nonconfirmatory) dose-finding study; no adjustments for multiple comparisons will be made.

Treatment Arms 9-11

As this is a Phase 2 (nonconfirmatory) dose-finding study, no adjustments for multiple comparisons for the secondary endpoints will be made. However, a hierarchical multiple comparisons procedure, which will control type I error in the primary endpoint analysis, will be implemented. The primary endpoints will be tested in a sequential manner at a 1-sided 0.025 significance level. The following is a list of the primary outcomes to be tested:

- Primary (Test 1) LY3853113 in combination with LY3819253 and LY3832479 compared to placebo for the proportion of participants with SARS-CoV-2 viral load greater than 5.27 on Day 7
- Primary (Test 2) LY3853113 alone compared to placebo for the proportion of participants with SARS-CoV-2 viral load greater than 5.27 on Day 7

6.6. Participant Disposition

The treatment and assessment period disposition and study disposition will be summarized for the safety population. Disposition summaries will be by treatment group. Summaries will also include reason for discontinuation from the study tabulated by treatment group.

All participants who are randomized and discontinued from study treatment or from the study will be listed, and the timing of discontinuing (from randomization) the study will be reported. If known, a reason for their discontinuation will be given.

In addition, a graphical summary (i.e., KM plot) of time from randomization to early permanent discontinuation of study or study treatment due to adverse events (AEs) may be generated if there are a substantial number of such events. This graphical summary would be by treatment group and include the log-rank test results.

Table PYAH.6.4. Tables and Figures Related to Disposition

Analysis	Details
Patient Disposition	Number and percentage of participants by reason for: • study discontinuation and • study treatment and assessment period discontinuation A column that combines all treatment groups (i.e., a total column) will be included (applicable to controlled analysis sets) No inferential statistics
Listing of study and study treatment disposition	
Listing of participants discontinuing due to a decision-related reason (loss to follow-up, patient decision, or investigator decision)	Variables included the reason for study discontinuation, the text collected in the specify field associated with the reasons for discontinuation, and the dates of discontinuation The text in the specified field should provide information to support that the reason is unrelated to efficacy or safety
Time to early discontinuation of study treatment due to adverse events (AEs)	Presented as a figure (if necessary)

6.7. Participant Characteristics

Participant demographic variables and baseline characteristics will be summarized by treatment and overall for the safety population. The continuous variables will be summarized using descriptive statistics and the categorical variables will be summarized using frequency counts and percentages. No inferential analysis for the comparability of baseline covariates across treatment groups will be performed. By-patient listings of basic demographic characteristics (i.e., age, sex, race, racial subgroup, ethnicity, and body weight) for the efficacy population will be provided.

Table PYAH.6.5. Tables and Figures Related to Demographics and Other Characteristics of Study Population

Baseline Demographic Characteristics Variables to be included: Age Age groups (<35, ≥35 to <45, ≥45 to <55, >55 years old) Race (American Indian or Alaska Native, Asian, Black or African American, Native, Hawaiian or Other Pacific Islander, White, Multiple) Ethnicity (Hispanic or Latino, Not Hispanic or Latino, Not Reported) Height Weight Body mass index (BMI), and Days since COVID-19 symptom onset. Days since COVID-19 symptom onset (≤8 days, >8 days) SpO₂ SpO₂ category (<96%, ≥96%) COVID-19 disease severity category Statistics to be included: Continuous: Mean, standard deviation, min, max, median, and first quartile and third quartile Categorical: n and percent (denominator for percentages will be the number of participants with nonmissing values) A column that combines all treatment groups (i.e., a total column) will be included (applicable to controlled analysis sets) No inferential statistics For Treatment Arms 12-14: The age groups are defined as:	Analysis	Details		
 Characteristics Age groups (<35, ≥35 to <45, ≥45 to <55, >55 years old) Sex Race (American Indian or Alaska Native, Asian, Black or African American, Native Hawaiian or Other Pacific Islander, White, Multiple) Ethnicity (Hispanic or Latino, Not Hispanic or Latino, Not Reported) Height Weight Body mass index (BMI), and Days since COVID-19 symptom onset. Days since COVID-19 symptom onset (≤8 days, >8 days) SpO₂ SpO₂ category (<96%, ≥96%) COVID-19 disease severity category Statistics to be included: Continuous: Mean, standard deviation, min, max, median, and first quartile and third quartile Categorical: n and percent (denominator for percentages will be the number of participants with nonmissing values) A column that combines all treatment groups (i.e., a total column) will be included (applicable to controlled analysis sets) No inferential statistics For Treatment Arms 12-14: • The age groups are defined as: 				
 Characteristics Age groups (<35, ≥35 to <45, ≥45 to <55, >55 years old) Sex Race (American Indian or Alaska Native, Asian, Black or African American, Native Hawaiian or Other Pacific Islander, White, Multiple) Ethnicity (Hispanic or Latino, Not Hispanic or Latino, Not Reported) Height Weight Body mass index (BMI), and Days since COVID-19 symptom onset. Days since COVID-19 symptom onset (≤8 days, >8 days) SpO₂ SpO₂ category (<96%, ≥96%) COVID-19 disease severity category Statistics to be included: Continuous: Mean, standard deviation, min, max, median, and first quartile and third quartile Categorical: n and percent (denominator for percentages will be the number of participants with nonmissing values) A column that combines all treatment groups (i.e., a total column) will be included (applicable to controlled analysis sets) No inferential statistics For Treatment Arms 12-14: • The age groups are defined as: 	Demographic			
 Sex Race (American Indian or Alaska Native, Asian, Black or African American, Native Hawaiian or Other Pacific Islander, White, Multiple) Ethnicity (Hispanic or Latino, Not Hispanic or Latino, Not Reported) Height Weight Body mass index (BMI), and Days since COVID-19 symptom onset. Days since COVID-19 symptom onset (≤8 days, >8 days) SpO₂ SpO₂ category (<96%, ≥96%) COVID-19 disease severity category Statistics to be included: Continuous: Mean, standard deviation, min, max, median, and first quartile and third quartile Categorical: n and percent (denominator for percentages will be the number of participants with nonmissing values) A column that combines all treatment groups (i.e., a total column) will be included (applicable to controlled analysis sets) No inferential statistics For Treatment Arms 12-14: The age groups are defined as: 				
Hawaiian or Other Pacific Islander, White, Multiple) • Ethnicity (Hispanic or Latino, Not Hispanic or Latino, Not Reported) • Height • Weight • Body mass index (BMI), and • Days since COVID-19 symptom onset. • Days since COVID-19 symptom onset (≤8 days, >8 days) • SpO₂ • SpO₂ category (<96%, ≥96%) • COVID-19 disease severity category Statistics to be included: Continuous: Mean, standard deviation, min, max, median, and first quartile and third quartile Categorical: n and percent (denominator for percentages will be the number of participants with nommissing values) A column that combines all treatment groups (i.e., a total column) will be included (applicable to controlled analysis sets) No inferential statistics For Treatment Arms 12-14: • The age groups are defined as:				
 Ethnicity (Hispanic or Latino, Not Hispanic or Latino, Not Reported) Height Weight Body mass index (BMI), and Days since COVID-19 symptom onset. Days since COVID-19 symptom onset (≤8 days, >8 days) SpO₂ SpO₂ category (<96%, ≥96%) COVID-19 disease severity category Statistics to be included: Continuous: Mean, standard deviation, min, max, median, and first quartile and third quartile Categorical: n and percent (denominator for percentages will be the number of participants with nonmissing values) A column that combines all treatment groups (i.e., a total column) will be included (applicable to controlled analysis sets) No inferential statistics For Treatment Arms 12-14: • The age groups are defined as: 		1 1 1 1 1 1 1 1 1 1 1 1 1 1 1 1 1 1 1 1		
 Height Weight Body mass index (BMI), and Days since COVID-19 symptom onset. Days since COVID-19 symptom onset (≤8 days, >8 days) SpO₂ SpO₂ category (<96%, ≥96%) COVID-19 disease severity category Statistics to be included: Continuous: Mean, standard deviation, min, max, median, and first quartile and third quartile Categorical: n and percent (denominator for percentages will be the number of participants with nonmissing values) A column that combines all treatment groups (i.e., a total column) will be included (applicable to controlled analysis sets) No inferential statistics For Treatment Arms 12-14: The age groups are defined as: 				
 Weight Body mass index (BMI), and Days since COVID-19 symptom onset. Days since COVID-19 symptom onset (≤8 days, >8 days) SpO₂ SpO₂ category (<96%, ≥96%) COVID-19 disease severity category Statistics to be included: Continuous: Mean, standard deviation, min, max, median, and first quartile and third quartile Categorical: n and percent (denominator for percentages will be the number of participants with nonmissing values) A column that combines all treatment groups (i.e., a total column) will be included (applicable to controlled analysis sets) No inferential statistics For Treatment Arms 12-14: • The age groups are defined as: 		Height		
 Body mass index (BMI), and Days since COVID-19 symptom onset. Days since COVID-19 symptom onset (≤8 days, >8 days) SpO₂ SpO₂ category (<96%, ≥96%) COVID-19 disease severity category Statistics to be included: Continuous: Mean, standard deviation, min, max, median, and first quartile and third quartile Categorical: n and percent (denominator for percentages will be the number of participants with nonmissing values) A column that combines all treatment groups (i.e., a total column) will be included (applicable to controlled analysis sets) No inferential statistics For Treatment Arms 12-14: The age groups are defined as: 				
 Days since COVID-19 symptom onset. Days since COVID-19 symptom onset (≤8 days, >8 days) SpO₂ SpO₂ category (<96%, ≥96%) COVID-19 disease severity category Statistics to be included: Continuous: Mean, standard deviation, min, max, median, and first quartile and third quartile Categorical: n and percent (denominator for percentages will be the number of participants with nonmissing values) A column that combines all treatment groups (i.e., a total column) will be included (applicable to controlled analysis sets) No inferential statistics For Treatment Arms 12-14: The age groups are defined as: 		· · · · · · · · · · · · · · · · · · ·		
 Days since COVID-19 symptom onset (≤8 days, >8 days) SpO₂ SpO₂ category (<96%, ≥96%) COVID-19 disease severity category Statistics to be included: Continuous: Mean, standard deviation, min, max, median, and first quartile and third quartile Categorical: n and percent (denominator for percentages will be the number of participants with nonmissing values) A column that combines all treatment groups (i.e., a total column) will be included (applicable to controlled analysis sets) No inferential statistics For Treatment Arms 12-14: • The age groups are defined as: 		• • • • • • • • • • • • • • • • • • • •		
 SpO₂ SpO₂ category (<96%, ≥96%) COVID-19 disease severity category Statistics to be included: Continuous: Mean, standard deviation, min, max, median, and first quartile and third quartile Categorical: n and percent (denominator for percentages will be the number of participants with nonmissing values) A column that combines all treatment groups (i.e., a total column) will be included (applicable to controlled analysis sets) No inferential statistics For Treatment Arms 12-14: The age groups are defined as: 				
 SpO₂ category (<96%, ≥96%) COVID-19 disease severity category Statistics to be included: Continuous: Mean, standard deviation, min, max, median, and first quartile and third quartile Categorical: n and percent (denominator for percentages will be the number of participants with nonmissing values) A column that combines all treatment groups (i.e., a total column) will be included (applicable to controlled analysis sets) No inferential statistics For Treatment Arms 12-14: The age groups are defined as: 				
• COVID-19 disease severity category Statistics to be included: Continuous: Mean, standard deviation, min, max, median, and first quartile and third quartile Categorical: n and percent (denominator for percentages will be the number of participants with nonmissing values) A column that combines all treatment groups (i.e., a total column) will be included (applicable to controlled analysis sets) No inferential statistics For Treatment Arms 12-14: • The age groups are defined as:				
Statistics to be included: Continuous: Mean, standard deviation, min, max, median, and first quartile and third quartile Categorical: n and percent (denominator for percentages will be the number of participants with nonmissing values) A column that combines all treatment groups (i.e., a total column) will be included (applicable to controlled analysis sets) No inferential statistics For Treatment Arms 12-14: • The age groups are defined as:				
Continuous: Mean, standard deviation, min, max, median, and first quartile and third quartile Categorical: n and percent (denominator for percentages will be the number of participants with nonmissing values) A column that combines all treatment groups (i.e., a total column) will be included (applicable to controlled analysis sets) No inferential statistics For Treatment Arms 12-14: • The age groups are defined as:		COVID 19 disease severity entegory		
Mean, standard deviation, min, max, median, and first quartile and third quartile Categorical: n and percent (denominator for percentages will be the number of participants with nonmissing values) A column that combines all treatment groups (i.e., a total column) will be included (applicable to controlled analysis sets) No inferential statistics For Treatment Arms 12-14: • The age groups are defined as:		Statistics to be included:		
Categorical: n and percent (denominator for percentages will be the number of participants with nonmissing values) A column that combines all treatment groups (i.e., a total column) will be included (applicable to controlled analysis sets) No inferential statistics For Treatment Arms 12-14: • The age groups are defined as:		Continuous:		
n and percent (denominator for percentages will be the number of participants with nonmissing values) A column that combines all treatment groups (i.e., a total column) will be included (applicable to controlled analysis sets) No inferential statistics For Treatment Arms 12-14: • The age groups are defined as:		Mean, standard deviation, min, max, median, and first quartile and third quartile		
nonmissing values) A column that combines all treatment groups (i.e., a total column) will be included (applicable to controlled analysis sets) No inferential statistics For Treatment Arms 12-14: • The age groups are defined as:				
A column that combines all treatment groups (i.e., a total column) will be included (applicable to controlled analysis sets) No inferential statistics For Treatment Arms 12-14: • The age groups are defined as:				
(applicable to controlled analysis sets) No inferential statistics For Treatment Arms 12-14: • The age groups are defined as:		,		
No inferential statistics For Treatment Arms 12-14: • The age groups are defined as:		(applicable to controlled analysis sets)		
For Treatment Arms 12-14: • The age groups are defined as:				
The age groups are defined as:		No inferential statistics		
The age groups are defined as:		For Treatment Arms 12-14:		
		o Age groups (<65, ≥65 years old), (≥12 to <18, ≥18 to <35, ≥35 to <45, ≥45 to <55, ≥55 to <65, ≥65 years old), (<65, ≥65 to <75, ≥75 to <85, ≥85 years		
• The following additional groups are defined:				
Baseline SARS-CoV-2 vaccine status				
SARS-CoV-2 vaccination during the study				
Medical History Number and percentage of participants with medical history events and preexisting	Medical History			
and Preexisting conditions using MedDRA PT nested within SOC	_			
conditions • Ordered by decreasing frequency within SOC on the LY total arm				
Preexisting conditions are defined as those conditions with a start date prior to the first doe		Preexisting conditions are defined as those conditions with a start date prior to the first dose		
		of the study drug and stop dates that are at or after the informed consent date or have no stop		
date (i.e., are ongoing).				
	Prior Therapy of	Number and percentage of participants with prior medication of interest will be displayed as		
Interest "Prior medications"	nterest	"Prior medications"		
Listing	Listing			
Demographics				

 $Abbreviations: \ max = maximum; \ MedDRA = Medical \ Dictionary \ for \ Regulatory \ Activities; \ min = minimum; \ MedDRA = Medical \ Dictionary \ for \ Regulatory \ Activities; \ min = minimum; \ MedDRA = Medical \ Dictionary \ for \ Regulatory \ Activities; \ min = minimum; \ MedDRA = Medical \ Dictionary \ for \ Regulatory \ Activities; \ min = minimum; \ MedDRA = Medical \ Dictionary \ for \ Regulatory \ Activities; \ min = minimum; \ MedDRA = Medical \ Dictionary \ for \ Regulatory \ Activities; \ min = minimum; \ MedDRA = Medical \ Dictionary \ for \ Regulatory \ Activities; \ min = minimum; \ MedDRA = Medical \ Dictionary \ for \ Regulatory \ Activities; \ min = minimum; \ MedDRA = Medical \ Dictionary \ for \ Regulatory \ Activities; \ min = minimum; \ MedDRA = Medical \ Dictionary \ for \ Regulatory \ Activities; \ min = minimum; \ MedDRA = Medical \ Dictionary \ for \ Regulatory \ Activities; \ min = minimum; \ MedDRA = Medical \ Dictionary \ for \ Regulatory \ Activities; \ min = minimum; \ MedDRA = Medical \ Dictionary \ for \ Regulatory \ Activities; \ min = minimum; \ MedDRA = Medical \ Dictionary \ for \ Regulatory \ Activities; \ min = minimum; \ MedDRA = Medical \ Dictionary \ for \ Regulatory \ for \ Regulat$

PT = preferred term; SOC = System Organ Class.

6.8. Treatment Compliance

As all study drug doses will be administered at the study site, treatment compliance will not be reported.

6.9. Prior Medication and Concomitant Therapy

Medications will be classified into anatomical therapeutic chemical (ATC) drug classes using the latest version of the WHO drug dictionary. Medication start and stop dates will be compared to the date of the first dose of treatment to allow medications to be classified as concomitant.

Prior medications are those medications that start and stop prior to the date of the first dose of study treatment. *Concomitant medications* are those medications that start before, on, or after the first day of study treatment and continue into the treatment and assessment period.

For all summary tables of concomitant medications, Preferred Terms of concomitant medication will be sorted by descending frequency in the LY total arm.

Table PYAH.6.6. Summary Tables Related to Concomitant Medications

Analysis	Details
Prior medications	Number and percentage of participants using Preferred Terms of prior medication
	Ordered by decreasing frequency
	No inferential statistics
Concomitant	Number and percentage of participants using Preferred Terms of concomitant medication
medications	Ordered by decreasing frequency
	No inferential statistics

6.10. Efficacy Analyses

The analysis of the viral load lab results will utilize the following conventions:

For qualitative endpoints in the trial (viral clearance yes/no, time to viral clearance) the lab determination of "positive"/"negative" will be used. SARS-CoV-2 clearance (yes/no) is defined as 2 consecutive negative tests for the SARS-CoV-2 virus. The date of viral clearance is defined as the earliest date of the 2 consecutive negative tests.

For quantitative endpoints in the trial (change from baseline, area under the response viral load curve [AUC]), the viral load will be derived based on cycle threshold (Ct) values with the following considerations:

- Two Ct values will be provided on 2 different genes: N1 and N2. N1 will be used as the primary measure; N2 will only be used when the Ct value for N1 is not available.
- Ct values range between 0 and 45.
- Negative CoV-2 tests will be associated with a Ct value of 45.
- For any sample with a positive CoV-2 test result, an additional normalization step will be taken in the analysis. The viral load Ct value described in the previous steps

will be subtracted by (RP Ct -26.17), where RP Ct is a measure for the amount of material in the sample, and 26.17 is a historical average value of RP Ct for this assay, used here to center the RP Ct values. This step will be skipped if a valid RP Ct value is unavailable for the sample.

• The (log base 10) viral load will be calculated from the Ct value (45-Ct)/log₂10, or (45-Ct)/3.321928.

A lower Ct value of 40 for negative CoV-2 tests may be explored as part of exploratory PK/PD exposure-response analysis (Section 6.11).

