5.1.2. Screening

Interested participants will sign the appropriate informed consent and child/adolescent assent document(s), as appropriate, prior to completion of any procedures. The participant may enter the study with a previous positive SARS-CoV-2 viral test result from an external testing facility. This test result must be the first time the participant has tested positive for SARS-CoV-2.

The investigator will review symptoms, risk factors and other non-invasive inclusion and exclusion criteria prior to any invasive procedures. If the participant is eligible after this review, then the site will perform the invasive procedures to confirm eligibility.

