6.1.3. Study Time Intervals

To calculate the length of any time interval or time period in this study, the following formula will be used:

 $Length\ of\ interval\ (days) = End\ Date - Interval\ Start\ Date + 1$

To convert any time length from days to weeks, the following formula will be used:

Length of interval (weeks) = Length of interval (days)/7

Only for the purpose of calculating the length of study period time intervals, the words "prior to" in Table PYAH.6.2 should be understood to mean "the day before" while the words "after" should be understood to mean "the day after." For the purpose of determining whether a date/time lies within an interval, these words are intended to convey whether the start or end of the period is inclusive of the specified date.

Study Period	Interval Start Definition	Interval End Definition
Screening: All participants who sign informed consent are considered as entering the Screening Period.	Informed consent date	Prior to the start of Treatment and Assessment Period.
Treatment and Assessment Period: All participants who are randomized to the study are considered as entering the treatment and assessment period.	At the start of study drug administration date/time following randomization. For participants who are randomized but not dosed, the treatment and assessment period starts on the date of randomization.	The minimum of treatment and assessment period discontinued date, study discontinuation date, or first post treatment follow-up visit date.
Post-Treatment Follow-Up: All participants who had a follow up visit are considered as entering follow-up period.	After the Treatment and Assessment Period ends.	The maximum of the last study visit date or study disposition date.

Table PYAH.6.2. Definition of Study Period Time Intervals

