6.10.3. Secondary Efficacy Analyses

6.10.3.1. SARS-CoV-2 Viral Load

6.10.3.1.1. Change from Baseline in SARS-CoV-2 Viral Load

Changes from baseline to Day 3, Day 5, Day 7, and Day 11 in SARS-CoV-2 viral load data in the log base 10 scale will be statistically analyzed using a linear mixed-effect model. The model will contain log base 10 transformed baseline as a covariate, treatment, day, treatment-by-day interaction) as fixed effects. The LS means and treatment differences (active treatment minus placebo) will be calculated and presented with their corresponding 95% CIs. In addition, the geometric mean ratio to baseline and corresponding standard error for each treatment, the ratio of geometric mean ratio to baseline vs placebo, and corresponding 95% CIs will be presented. All available data will be used in the analysis.

SARS-CoV-2 viral load, including changes from baseline, will be summarized and plotted by treatment and listed. Baseline is defined as the Day 1 predose assessment.

No imputations of missing data will be conducted.

6.10.3.1.2. SARS-CoV-2 Viral Load Among Participants Enrolled with ≤8 Days of Symptoms Prior to Randomization

Similar methodology, as described in Section 6.10.1, will be utilized on the subset of participants enrolled with ≤ 8 days of symptoms prior to randomization.

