6.10.3.1.5. SARS-CoV-2 Clearance

See Section 6.10 for more details on the definition of viral clearance.

The proportion of participants that achieve SARS-CoV-2 clearance at Days 3, 5, 7, 11, and 29 will be summarized by treatment in frequency tables and listed.

In addition, the number of participants that achieve SARS-CoV-2 clearance at Days 3, 5, 7, 11, and 29 will be analyzed using logistic regression to compare active treatment versus placebo at each dose level.

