6.10.3.1.6. Time to SARS-CoV-2 Clearance

See Section 6.10 for more details on the definition of viral clearance and date of viral clearance.

Time to SARS-CoV-2 clearance is defined (in days) as:

(Date when SARS-CoV-2 clearance status is first changed to "Yes" – Infusion Date + 1)

If a patient has not experienced SARS-CoV-2 clearance by completion or early discontinuation of study/study treatment and assessment period, the patient will be censored at the date of their last visit during the treatment and assessment period.

Time to SARS-CoV-2 clearance will be evaluated during the study treatment and assessment period only, and will be summarized by treatment and listed. Cox proportional hazard model will be used.

Time to SARS-CoV-2 clearance will be presented graphically.

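### Clearance analyses do not require a positive Day 1 swab, so participants already negative before dosing can count as clearance successes and dilute the placebo comparisons in Arms 1-11

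*SAP*

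**What the plan says.** Section 6.10 gives the definition: "SARS-CoV-2 clearance (yes/no) is defined as 2 consecutive negative tests for the SARS-CoV-2 virus". It then dates the event: "The date of viral clearance is defined as the earliest date of the 2 consecutive negative tests". Neither sentence mentions baseline status or the time of dosing.

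The sections that use the definition add no such condition:

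- Table PYAH.6.1: the Efficacy population needs randomization, dosing and one postbaseline viral load. A positive baseline swab is not required.
- Section 6.3.1 (mNRI): two earlier consecutive negatives turn a missing status into Yes, and all participants are kept.
- Section 6.10.3.1.5: "The proportion of participants that achieve SARS-CoV-2 clearance at Days 3, 5, 7, 11, and 29 will be summarized by treatment", followed by logistic regression against placebo. Under Section 6.1.4 the binary model contains treatment only.

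Time to clearance (Section 6.10.3.1.6) starts from "Date when SARS-CoV-2 clearance status is first changed to" Yes, subtracts the infusion date and adds 1. The same section says: "Time to SARS-CoV-2 clearance will be evaluated during the study treatment and assessment period only". Table PYAH.6.2 begins that period "At the start of study drug administration date/time following randomization", and Section 6.10.3.1.1 says of viral load: "Baseline is defined as the Day 1 predose assessment".

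On entry, Section 5.1.2 says: "The participant may enter the study with a previous positive SARS-CoV-2 viral test result from an external testing facility". The study's own Day 1 swab therefore need not be the qualifying test.

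**The concern.** A clearance endpoint should describe people who carry detectable virus when treated and then lose it. Someone who qualified on an earlier external test may be negative on the Day 1 predose swab. If that person is also negative on Day 3, the definition is met by a pair whose first member precedes the drug. Even if the predose swab is ignored, negatives on Days 3 and 5 meet it. Such a participant is a success whichever arm they are in.

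Randomization spreads these participants evenly in expectation. They therefore do not favour an arm, but they add the same block of treatment-unrelated successes to both sides. Contrasts with placebo move toward no difference, and reported clearance rates rise. Clearance at Days 3, 5, 7, 11 and 29 and time to clearance are secondary endpoints in every set of arms.

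**Working it through.** **No stated figure to reproduce.** The SAP gives no rate, power or sample size for clearance. As a check of the power formula only, take the Arms 7-8 primary endpoint: 5% against 19%, 100 per arm, two-sided 0.05. With p̄ = 0.12,

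power = Φ{[0.14 − 1.96·√(2·0.12·0.88/100)] / √[(0.05·0.95 + 0.19·0.81)/100]} = 86.7%,

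close to the SAP's figure of greater than 87%.

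**Dilution of the yes/no endpoint.** Let f be the baseline-negative share and p the clearance rate among baseline-positives. If all baseline-negatives count as cleared, each arm's rate becomes p' = f + (1−f)p, so

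p'₁ − p'₀ = (1−f)(p₁ − p₀).

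This factor needs no assumption about p. The rest is illustrative: f and the clearance rates are assumed, and 100 per arm is the planned size of Arms 7 and 8. The last column drops the baseline-negatives and pays for it with n = 100(1−f).

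| p₀ v p₁ | f | Rates as written | Difference | Odds ratio | Power as written | Power, baseline-positives only |
|---|---|---|---|---|---|---|
| 25% v 45% | 0 | 25.0% v 45.0% | 0.20 | 2.45 | 85% | 85% |
| | 5% | 28.75% v 47.75% | 0.19 | 2.26 | 79% | 83% |
| | 10% | 32.5% v 50.5% | 0.18 | 2.12 | 74% | 81% |
| | 15% | 36.25% v 53.25% | 0.17 | 2.00 | 68% | 79% |
| 10% v 25% | 0 | 10.0% v 25.0% | 0.15 | 3.00 | 80% | 80% |
| | 10% | 19.0% v 32.5% | 0.135 | 2.05 | 59% | 76% |

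**An early visit with a modest effect.** Assume 30% of baseline-positive placebo participants clear by Day 11 and a hazard ratio of 1.4. Then λ = −ln(0.7)/10 = 0.0357 per day. After 2 days at risk, clearance is 1 − exp(−2λ) = 6.9% on placebo and 1 − exp(−2.8λ) = 9.5% on active treatment, an odds ratio of 1.42. At f = 5% the rates are 11.5% and 14.0% (1.25). At f = 10% they are 16.2% and 18.6% (1.18). The risk difference moves only from 2.6 to 2.5 and 2.4 points, so the odds ratio is where the effect shows.

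**Time to clearance.** For a participant negative on Days 1, 3 and 5:

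- Dating rule alone: Day 1 − Day 1 + 1 = 1 day.
- Restriction to the period that starts at dosing: the predose swab drops out, and the event is at Day 3 − Day 1 + 1 = 3 days.

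The SAP does not say which applies. In a simulated Cox fit (4,000 per arm, swab days 3, 5, 7, 11 and 29, control median 14 days, true hazard ratio 1.5, Breslow ties), the estimate on this coarse grid is about 1.36 with no baseline-negatives. At f = 10% it is about 1.32 if they are events at Day 1 and 1.30 if at Day 3, against about 1.35 if they are excluded. The attenuation is small and similar on either reading.

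**The case against.** The strongest reply is that the all-participant analysis is a legitimate choice. It keeps everyone as randomized, mNRI is meant to retain all participants, and balanced baseline status does not inflate the false-positive rate. Restricting to baseline-positives answers a question about a different population. This stands as far as validity goes: the comparison is diluted, not invalid. It does not justify counting a state that preceded dosing as clearance, and a filter on a predose swab keeps the randomized comparison intact.

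The frequency is unknown. The SAP shows neither how old the external test may be nor any limit on symptom duration. The stratum above 8 days shows only that such participants were anticipated, and the Ct 45 convention covers negatives at any visit. So f may be near zero. This stands in full.

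The early-visit example also changes little in practice: 6.9% against 9.5% at 100 per arm has only about 10% power before any dilution.

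Three stronger readings are tempting and are not supported:

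- A reader might infer that every baseline-negative participant is an event at 1 day. That follows from the dating rule alone. The restriction to the treatment and assessment period points to the first post-dose negative, so this is an unresolved ambiguity.
- A reader might infer that every clearance comparison is affected. Arms 12-14 have none; Section 6.1.4 makes them descriptive.
- A reader might infer that the main result is at risk. The primary endpoint, viral load above 5.27 on Day 7, does not use the clearance definition.

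**Conclusion.** The point holds for the secondary clearance endpoints. No section requires a positive Day 1 swab, and for the yes/no endpoint and mNRI none requires post-dose negatives. For time to clearance, Sections 6.10, 6.10.3.1.6 and 6.1.3 leave open when a predose negative is counted; either way the event is uninformative about treatment.

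In Arms 1-11 the risk difference shrinks by 1−f when baseline-negatives all count as cleared, with the largest loss on the odds-ratio scale at early visits. In Arms 12-14 only the descriptive rates are inflated. The size rests on f and on clearance rates that the documents do not give. At assumed f of 5% to 15% and 25% against 45% clearance, the plan as written has about 4 to 11 percentage points less power than the baseline-positive analysis (79% v 83%, 68% v 79%). At f = 0 nothing is lost. Because these are secondary endpoints without multiplicity control in a study the SAP calls nonconfirmatory, this should be corrected but does not threaten the main conclusion.

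**What to change.** In Sections 6.3.1, 6.10, 6.10.3.1.5 and 6.10.3.1.6:

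- Run the clearance analyses in Efficacy-population participants whose Day 1 predose swab is positive.
- State that both negative tests must be post-dose, in the same words for the yes/no endpoint, mNRI and time to clearance. Within the baseline-positive set this adds little, but it settles the dating conflict and governs the all-participant version too.
- Report the number of baseline-negative participants by arm.
- Keep the all-participant analysis as a sensitivity table.

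One detail must accompany this. The SAP should say whether status on a given day uses only swabs up to that day or follows the back-dated clearance date. The swab days it lists up to Day 11 are 1, 3, 5, 7 and 11, so with post-dose negatives required nobody could be cleared at Day 3 under the first reading.

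The cost is a few lines of wording, one baseline filter and a slightly smaller denominator. Swab status before dosing cannot be affected by treatment, so the filter introduces no bias between arms.
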